10.3. Subject Status and Classification

All subjects who complete the informed consent process, sign and date the ICF are considered enrolled. Subject status will be classified as below after enrollment:

Intent: Refers to a subject who meets all eligibility and signs the consent, but does not get randomized. This classification status also refers to:

- A subject who no longer meets eligibility criteria at the time of randomization
- A subject who is no longer willing to participate in the study

The original ICF and screening documentation for intent subjects must be maintained in the Center's files and an End of Study form is to be completed. Patients shall be withdrawn from the study and followed per standard of care. No further follow-up is required. Intent patients will not count towards the enrollment ceiling.

Treatment: Refers to a subject who has been enrolled and their device has been reprogrammed to the arm that they have been randomized to (ATP and Shock or Shock Only.)

10.4. Enrollment Controls

Each center may enroll up to a maximum of 260 subjects. If a center wishes to exceed this limit, the center must obtain prior written approval from the sponsor or sponsor's delegated representative.

Subjects consented, but who do not undergo a randomization/programming to either treatment arm, will not count towards the 2,600 patients. Patients already consented at time of notification shall still be entered in the database and withdrawn from the study.

Investigational sites will be notified when the enrollment goal is close to being reached and once enrollment is complete.

11. Study Methods

11.1. Data Collection

The data collection schedule for this study is aligned with standard of care (SOC) practices at centers. Therefore, there are two data collection schedules for subjects: 1.) Subjects who are not monitored on LATITUDE and 2.) Subjects who are monitored on LATITUDE.

Table 11.1-1 for subjects who are NOT monitored on LATITUDE

Table 11.1-2 for subjects who are monitored on LATITUDE

Table 11.1-1 Data Collection Schedule – Subjects NOT on LATITUDE

Procedure/ Assessment	Enrollment (≤ 60 calendar days post successful implant)	Randomizatio n (Obtained day of device programming to assigned treatment arm)	Programing to Assigned Treatment Arm (Day 0) (Day of randomization. Cannot exceed 60 calendar days post implant)	Follow Up Visits through 5 years 6 Mo: 180±60 d 12 Mo: 360±60d 18 Mo:540±60d 24 Mo: 720±60 d 30 Mo: 900±60d 36 Mo: 1080±60d 42 Mo: 1260±60 d 48 Mo: 1440±60d 54 Mo: 1620±60d 60 Mo: 1800+30d	Unscheduled Visits (within 30 calendar days of therapy delivery)
Informed consent process, including informed consent signature and date	X				
Inclusion/Exclusion	X	♦			
ECG Upload—Standard of Care (recommended not required)			SOC		
Physical assessment			X		
Demographics	X				
Medical History			X		
Cardiac Medications			X	X**	X**
Randomization – obtained via the EDC system/Risk Stratifiers		X			
Device Interrogation/ Programming Status			X	X	X
Reportable AE's		*	*	*	*
Arrhythmia Episodes		*	*	*	*

Legend: X= Required; *=Data required only if the event occurred; SOC=Recommended if Center Standard of Care, **= Need to document changes to cardiac meds only, ◊= Sites must verify subject still meets inclusion/exclusion criteria prior to randomization

Table 11.1-2 Data Collection Schedule – Subjects ON LATITUDE

Study Reference Number C1924

Confidential

Procedure/Assessment	Enrollment (≤60 calendar days post implant)	Randomization (Obtained day of device programming to assigned treatment arm)	Programing to Assigned Treatment Arm (Day 0) (Day of randomization. Cannot exceed 60 calendar days post implant)	LATITUDE Follow Up Data (Automatic Device Report Upload) Done by Sponsor 6 Mo: 180±60 d 18 Mo:540±60d 30 Mo: 900±60d 42 Mo: 1260 ±60 d 54 Mo: 1620 ±60 d	Subject Phone Call Visit Done by Center 6 Mo: 180±60 d 18 Mo:540±60d 30 Mo: 900±60d 42 Mo: 1260 ±60 d 54 Mo: 1620 ±60d	Follow Up Visits (In Clinic) 12 Mo: 360±60d 24 Mo: 720±60 d 36 Mo: 1080±60d 48 Mo: 1440 ± 60d 60 Mo: 1800+30d	Unscheduled Visits (per Physician Discretion as SOC)
Informed consent process, including informed consent signature and date	X						
Inclusion/Exclusion	X	◊					
ECG Upload – Standard of Care (recommended, not required)			SOC				
Physical assessment			X				
Demographics	X						
Medical History			X				
Cardiac Medications			X		X**	X**	X**

Boston Scientific APPRAISE ATP CIP 91165305 Ver AB Page 27 of 72

Randomization – obtained via the EDC system/Risk Stratifiers	X					
Device Interrogation/						
Programming Status		X	LAT		X	X
Reportable AE's						
•	*	*		*	*	*
Arrhythmia Episodes	*	*	LAT*		*	*

Legend: X= Required; *=Data required only if the event occurred; **SOC**=Recommended if Center Standard of Care; **LAT**= Required if subject is on LATITUDE remote monitoring. Report will be uploaded by Latitude BSC team; **= Need to document changes to cardiac meds only;

 \Diamond = Sites must verify subject still meets inclusion/exclusion criteria prior to randomization

11.2. Study Candidate Screening

Any subject meeting all of the inclusion criteria and not meeting any of the exclusion criteria is enrollment eligible for the APPRAISE ATP study. A formal screening log is not required to be maintained.

11.3. Informed Consent and Enrollment

Subjects who meet all of the inclusion criteria, none of the exclusion criteria, and undergo the informed consent process, sign, and date the informed consent form are considered enrolled in the study. No data collection, data entry, or study specific procedure shall be performed prior to having appropriately consented the patient. Table 11.3.-1 lists the data collection requirements at the enrollment visit.

Table 11.3-1: Source Documentation Requirements – Enrollment Visit

Data Collection Requirement	Retention of Original Source Documentation
Informed Consent Form and princluding informed consent and signature date	·
Inclusion/Exclusion CriteriaDemographics	

11.4. Randomization Assignment

Randomization by the EDC system and device programming to randomized treatment arm can be performed at the enrollment visit once the patient has completed the informed consent process. Randomization will be obtained through the EDC system. Subject data regarding ischemic etiology, history of atrial fibrillation and diabetes must be entered in the EDC database as randomization cannot occur without these three data points.

If randomization and subsequent device programming to randomized arm is not performed at the enrollment visit, the randomization and device programming visit must occur on the same day, and cannot exceed 60 calendar days post implant. Prior to randomization, sites need to verify that subjects still meet inclusion criteria and no exclusion criteria.

Every reasonable attempt will be made to have subjects blinded to their randomized treatment arm assignment throughout the trial.

Table 11.4-1: Source Document Requirements – Randomization

Data Collection Requirement	Retention of Original Source Documentation
Subject randomization assignment	Investigational Center
• Reportable AE's, if applicable	

11.5. Programming to Treatment Arm – Index Procedure (Day 0)

If the subject's device was not programmed to the randomized treatment arm assignment at the enrollment visit, programming to the randomized arm must be done the same calendar day of obtaining the randomization assignment, and cannot exceed 60 calendar days post implant. The date the device was programmed to the randomized arm will be considered the time of origin: Index Procedure Day 0, for the subject. Subsequent follow up visits will be based off of this date. Once a subject is programmed to the randomized arm, the subject will remain in the assigned treatment arm until the end of the study to follow the methodology of intention-to-treat (ITT).

Tasks to be performed at this visit include:

- Pulse generator interrogation with routine lead evaluation on implanted RA and RV leads which includes:
 - o Intrinsic sensing (mV)
 - o Pacing impedance (Ω)
 - \circ Shock lead impedance (Ω)
 - o Pacing threshold (V) (pulse width at physician discretion)
- Arrhythmia logbook evaluation
 - Verify subject has not had any spontaneous ventricular rhythms that were treated with a shock
- Programming the device to the subject's randomized treatment arm

Devices are required to be programmed according to this protocol. Table 11.5-1 represents the required device programming for subjects who are randomized to Arm 1: ATP and Shock.

Table 11.5-1: Required Programming: Arm 1: ATP and Shock

ARM 1 = ATP and Shock				
77	Programming			
Ventricular Zones	3			
Zone 1: (VT-1) Rate	170 bpm			
Zone 1: (VT-1) Initial Duration	12 seconds			
Zone 1: (VT-1) Therapy	Monitor Only (disable all therapy)			
Zone 2: (VT) Rate	200 bpm			
Zone 2: (VT) Initial Duration	12 seconds			
Zone 2: (VT) Redetection Duration	1.0 second (nominal)			
Zone 2: (VT) Post-Shock Duration	1.0 second (nominal)			
Zone 2: (VT) Rhythm Detection Enhancement Type	ON (Detection enhancement type is per Investigator Discretion)			
Zone 2: (VT) Therapy	All shocks: 41 Joules			
ATP1				
Number of Bursts	1			
Pulses per Burst				
Initial	8			
Increment	0			
Coupling Interval	88%			
Burst Cycle Length	88%			
Ramp Decrement	0			
Minimum Interval	220 ms			
ATP2	OFF			
	1			
Zone 3: (VF) Rate	250			
Zone 3: (VF) Initial Duration	5 seconds			
Zone 3: (VF) Redetection Duration	1.0 second			
Zone 3: (VF) Post-Shock Duration	1.0 second			
Zone 3: (VF) QUICK CONVERT ATP	OFF			
Zone 3: (VF) Therapy	All shocks: 41 Joules			

Table 11.5-2 represents the required device programming for subjects who are randomized to Arm 2: Shock only.

Table 11.5-2: Required Programming: Arm 2: Shock Only

ARM 2 = Shock Only	Programming
Ventricular Zones	3
Zone 1: (VT-1) Rate	170 bpm
Zone 1: (VT-1) Initial Duration	12 seconds
Zone 1: (VT-1) Therapy	Monitor Only (disable all therapy)

Zone 2: (VT) Rate	200 bpm
Zone 2: (VT) Initial Duration	12 seconds
Zone 2: (VT) Redetection Duration	1.0 second (nominal)
Zone 2: (VT) Post-Shock Duration	1.0 second (nominal)
Zone 2: (VT) Rhythm Detection Enhancement Type	ON: (Detection enhancement type is per Investigator Discretion)
Zone 2: (VT) Therapy	All shocks: 41 Joules
ATP1	OFF
ATP2	OFF

Zone 3: (VF) Rate	250 bpm
Zone 3: (VF) Initial Duration	5 seconds
Zone 3: (VF) Redetection Duration	1.0 second
Zone 3: (VF) Post-Shock Duration	1.0 second
Zone 3: (VF) QUICK CONVERT ATP	OFF
Zone 3: (VF) Therapy	All shocks: 41 Joules

Bradycardia Pacing: Brady pacing programming in either treatment arm will be at the Investigator Discretion. It is recommended that brady programming for single chamber devices is VVI 40 and for dual chamber devices DDD with RHYTHMIQTM or AV Search + (± rate response).

Source data requirements at Index Procedure: Programming to Treatment Arm is described in Table 11.5-3.

Table 11.5-3: Source Documentation Requirements – Index Procedure (Day 0)

Programming to Treatment Arm Visit

Data Collection Requirement	Retention of Original Source Documentation
 Reportable Adverse Events, Device Deficiencies, and Protocol Deviations, if applicable Physical Assessment 	Investigational Center
Medical History	
Cardiac Medications	
 Device Follow Up Report Selected Episode Electrograms, as applicable Device Settings Report Settings Change Report Arrhythmia log book 	Printed copy of all final reports retained at Investigational Center Save to USB for Investigational Site. Copy will be sent to sponsor, if applicable Upload USB into EDC system
Baseline ECG – most recent, SOC* * NOTE: An ECG is not required to be performed. It is highly recommended that the patient's most recent ECG, performed as SOC, be uploaded into the EDC system as available.	Upload ECG into EDC system if available

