8.2. Treatment Assignment

Any patient meeting all inclusion and no exclusion criteria is enrollment eligible for the APPRAISE ATP study. Patients are considered enrolled in the study once the informed consent form (ICF) has been executed.

Randomization schemes can be obtained by logging onto the electronic data capture system (EDC) and registering the patient. Randomization will be in a 1:1 ratio of either treatment arm and will be stratified by ischemic etiology, history of atrial fibrillation, and diabetes.

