11.7. Subjects who are monitored on LATITUDE

For subjects who are remotely monitored, the wireless LATITUDE[™] Patient Management system will be utilized to collect and store treated tachyarrhythmia episodes. Alerts, diagnostic data, and all treated ventricular episodes EGMs are collected for endpoint evaluation directly from the LATITUDE database. Applicable reports will be uploaded remotely into the study database from the LATITUDE BSC team as defined on the data collection schedule on Table 11.1-2.

After programming to treatment arm (Index procedure Day 0), subjects who are remotely monitored with the LATITUDE system must have the following yellow alerts programmed on in the LATITUDE database:

- Ventricular shock therapy delivered to convert arrhythmia
- Accelerated ventricular arrhythmia episode
- Atrial Arrhythmia burden of at least {>1, 3, 6, 12, 18, or 24} hours in a 24 hour period
- Patient triggered event stored

If the HeartLogic feature is available in the implanted device, all subjects with this feature will be monitored by the LATITUDE BSC team for the specific HeartLogic alerts. In the event of an alert, a report will be uploaded by the LATITUDE BSC team into the study database.

Table 11.7-1: LATITUDE Follow Up Data – Device Report Upload

Data Collection Requirement	Retention of Original Source Documentation
LATITUDE Nominal Device ReportVentricular arrhythmia episodesLATITUDE Alerts	Reports uploaded into the study database by BSC LATITUDE team

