12.2.2. Control of Systematic Error/Bias

Overall Type I error for the Primary Endpoint will not exceed 5%. Type I error will be split and managed for the interim superiority analyses by employing an O'Brien-Fleming-type error spending function. Superiority testing for each group will be performed with an overall Type I error of 2.5%, resulting in a total of 5% across both groups. As described in Section 12.1.1.3, in the event that equivalency is not established, Type I error will be controlled for the additional superiority test per gating methodology and will not require further multiplicity adjustments

To reduce the possible introduction of selection bias, subjects will be randomized to their treatment assignment. To reduce the possible introduction of observer bias, an objective primary outcome of device-recorded all-cause shocks will be evaluated. To reduce the possible introduction of classification bias for the secondary endpoints of appropriate and inappropriate shocks, shocks will be adjudicated by an independent electrogram adjudication core lab.

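### The Zone 2 detection enhancement type is left to an investigator who can know the arm, and nothing fixes or records the choice before randomization

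*Combined protocol and SAP*

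**What the plan says.** Tables 11.5-1 and 11.5-2 set the zone rates, durations, shock energy and ATP parameters for each arm. For Zone 2 the enhancement must be on, but its type is open: "ON (Detection enhancement type is per Investigator Discretion" in Arm 1 and "ON: (Detection enhancement type is per Investigator Discretion" in Arm 2. Table 8.2-2 shows that Zone 2 is the only zone in which the arms differ.

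On timing, Section 11.5 says that "programming to the randomized arm must be done the same calendar day of obtaining the randomization assignment". On blinding, Section 11.4 says only that "Every reasonable attempt will be made to have subjects blinded to their randomized treatment arm assignment throughout the trial". Three baseline facts must be in EDC before randomization can occur, and the enhancement type is not one of them. Section 8.2 says that randomization "will be stratified by ischemic etiology, history of atrial fibrillation, and diabetes". The primary Cox model (12.1.1.3) has programming scheme as its covariate. Against observer bias, Section 12.2.2 says that "an objective primary outcome of device-recorded all-cause shocks will be evaluated". It adds core-laboratory adjudication of appropriate and inappropriate shocks.

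**The concern.** The detection enhancement bears on whether a fast rhythm in Zone 2 is treated or withheld. Whoever switches ATP on or off must know the arm, and that person may set or change the enhancement type in the same session. An investigator uneasy about a patient without ATP could pick a more restrictive type in the shock-only arm. The opposite pattern is also possible.

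All-cause shock includes inappropriate shocks, so such a pattern would enter the primary hazard ratio directly. Randomization cannot balance a choice made after it. A device-recorded outcome and adjudication protect how shocks are counted and classified, not whether one is delivered. In an equivalence trial the bias can work either way: it can pull a true difference inside the margins, or push a true null result towards one of them.

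**Working it through.** **Inputs from the documents.** Margins 0.65 and 1/0.65 = 1.54, N = 2600, 90% power, 10% attrition at 18 months, 42 months of enrollment (12.1.1.2). Final-look significance level 0.022 (12.3.1). About 5% appropriate and 3% inappropriate shocks in the earlier programming trial described in the Introduction, which gives an inappropriate share of 3/8.

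**Reproducing the plan's size.** Events for two one-sided tests at a true ratio of 1: 4(z₀.₉₇₈ + z₀.₉₅)² / ln(0.65)² = 4(2.014 + 1.645)² / 0.4308² = 288.6. The time unit of the 6% and 7% shock rates is not stated. Read as 18-month rates, with uniform accrual and exponential attrition, 2600 subjects yield 288.1 events (Scenario 1) and 289.7 (Scenario 2). The required N is 2604 and 2590. Read as annual rates they give about 418 to 420 events and 98% power, which does not match the plan. I use 288 events.

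**Decision rule.** SE of the log hazard ratio = 2/√288 = 0.1179. Equivalence requires |log HR estimate| < 0.4308 − 2.014 × 0.1179 = 0.1934. For a true log ratio θ, P(equivalence) = Φ[(0.1934 − θ)/0.1179] − Φ[(−0.1934 − θ)/0.1179].

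**Effect of a cut r in inappropriate shocks in the shock-only arm.**
- True ratio 1.0: HR = 5/8 + (3/8)(1 − r).
- True ratio 1.54, with all the excess in appropriate shocks: HR = 1.538 − (3/8)r.
- True ratio 1.54, with the excess shared proportionally: HR = 1.538 × [5/8 + (3/8)(1 − r)].

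| r | True 1.0: HR, power | True 1.54, excess all appropriate: HR, false equivalence | True 1.54, excess shared: HR, false equivalence |
|---|---|---|---|
| 0 | 1.00, 89.9% | 1.54, 2.2% | 1.54, 2.2% |
| 4% | 0.985, 89.6% | 1.52, 2.7% | 1.52, 3.0% |
| 12.5% | 0.953, 87.1% | 1.49, 4.0% | 1.47, 5.4% |
| 20% | 0.925, 82.6% | 1.46, 5.6% | 1.42, 8.8% |
| 30% | 0.888, 73.1% | 1.43, 8.5% | 1.37, 15.8% |

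**Where the values of r come from.** All are assumptions. Suppose 40% of one arm gets a restrictive type and 50% to 60% of the other does, and the less restrictive type carries 1.5 to 2 times the inappropriate-shock hazard. The smallest cut is 1 − (0.5 + 0.5 × 1.5)/(0.4 + 0.6 × 1.5) = 1 − 1.25/1.30 = 3.8%. The largest is 1 − (0.6 + 0.4 × 2)/(0.4 + 0.6 × 2) = 1 − 1.4/1.6 = 12.5%. The 20% and 30% rows are arm-wide cuts that nothing in the documents supports; they mark an outer range.

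**Reach.** To carry a true ratio of 1.0 to a margin by this route alone, the inappropriate-shock hazard ratio between arms would have to be (1.538 − 0.625)/0.375 = 2.44 or (0.65 − 0.625)/0.375 = 0.07.

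**The case against.** The rule is the same in both arms, so differential use is a risk and not a feature of the plan. Implant may precede Day 0 by up to 60 days, and the documents do not say whether a type already set is kept. The type may therefore often be settled before the arm is known. This stands as a limit on confidence, but no text requires the earlier setting to be kept.

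The sizes are soft. The 3/8 share is an upper figure, because the tables list the enhancement only for Zone 2 and inappropriate shocks in Zone 3 would not respond to it. The 5% and 3% come from a trial with half CRT-D devices. According to the Introduction, its shock incidence was similar across three programming arms. Those arms did not test enhancement type, but they lend no support to a large effect.

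Part of the safeguard exists. Device Settings and Settings Change Reports are collected, Section 11.9 requires reprogramming and its reason to be recorded, and inappropriate shock is a separate adjudicated endpoint. An imbalance could thus be seen afterwards, but no tabulation by arm is planned, and seeing it would not remove it from the primary hazard ratio.

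A reader might extend the point in two ways that the documents do not support. First, Section 11.7 says that LATITUDE subjects "must have the following yellow alerts programmed on in the LATITUDE database", among them "Atrial Arrhythmia burden of at least {>1, 3, 6, 12, 18, or 24} hours in a 24 hour period". No one is named as choosing the level, and the alert is a notification, not a therapy setting in the Section 11.5 tables. Any effect would be indirect and confined to LATITUDE subjects. Second, cardiac medications are first recorded at Day 0, so a drug change made in reaction to the assignment could pass as baseline. Medications do not enter the primary Cox model, and nothing suggests that drugs are changed because of the arm.

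**Conclusion.** The gap is real and narrow: one discretionary tachyarrhythmia setting, in the only zone where the arms differ, may be chosen by someone who knows the arm, and no entry made before assignment shows what would have been chosen otherwise.

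The size is hypothetical. Under the stated assumptions, false equivalence at the margin is about 3% to 9% (up to 16% with a shared excess) against 2.2%, and power at a true ratio of 1.0 is about 90% to 73%. With the modest imbalances that give r of 4% to 12.5%, the figures are 2.7% to 5.4% and 90% to 87%. It would be wrong to infer that the choice will differ by arm, or that this route alone would plausibly carry a true ratio of 1.0 to a margin. The case for acting is that the protection costs very little.

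**What to change.** In Sections 11.4 and 11.5, require the site to enter the intended Zone 2 enhancement type and its settings in EDC before the assignment is released, beside the three entries already mandatory there. Require that choice to be programmed whichever arm is assigned. The investigator's discretion over the choice is unchanged; only its timing moves.

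State that any later change of type is recorded as dated reprogramming with its reason. Section 11.9 is headed as covering reprogramming outside the plan, so a switch between permitted types might otherwise be thought exempt. Add a table of pre-assignment and Day 0 enhancement type by arm, drawn from the EDC entry and the settings reports already collected.

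Cost: one or two EDC fields, a sentence or two in 11.4 and 11.5, one table, and a few minutes of site work per subject. Sample size, margins and the primary model stay as they are.

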11.6. Semi-Annual Follow-up Visits

11.6.1 Subjects who are **NOT** monitored on LATITUDE:

After programming to treatment arm (Index procedure: Day 0), scheduled in-clinic visits are required to be performed at 180 day intervals (± 60days) from the programming (Day 0) date (i.e. 6 Mo: 180±60d; 12 Mo: 360±60d; 18 Mo: 540±60d, etc.) in order to capture new, not previously reported:

- Ventricular arrhythmia episodes
- Reportable adverse events

- Device programming changes
- Protocol deviations
- Device Deficiencies
- Cardiac medication changes

Tasks to be performed at the in-clinic follow-up visits include:

- Pulse generator interrogation with routine lead evaluation on implanted RA and RV leads which includes:
 - o Intrinsic sensing (mV)
 - o Pacing impedance (Ω)
 - \circ Shock lead impedance (Ω)
 - o Pacing threshold (V) (pulse width at physician discretion)
- Arrhythmia logbook evaluation
 - o Print applicable arrhythmia episodes
- Save interrogation session to USB
- Upload into EDC system

Source data requirements at the Semi-Annual Follow-Up Visits for subjects who are not monitored on LATITUDE are described in Table 11.6-1

Table 11.6-1: Source Documentation Requirements - Follow Up Visits
Subjects NOT on LATITUDE

Data Collection Requirement	Retention of Original Source Documentation
 Reportable Adverse Events, Device Deficiencies, and Protocol Deviations, if applicable Cardiac Medication Changes 	Investigational Center
 Device Follow Up Report Selected Episode Electrograms, as applicable Device Settings Report Settings Change Report 	Printed Copy of all final reports retained at Investigational Center Save to USB for Investigational Site. Copy will be sent to sponsor, if applicable

Table 11.6-1: Source Documentation Requirements - Follow Up Visits
Subjects NOT on LATITUDE

Data Collection Requirement	Retention of Original Source Documentation
Arrhythmia log book	Upload USB into EDC system

